7.3 Trial treatment

- Number of treatments administered
- Treatment compliance/tolerance including reasons for early discontinuation or protocol violations, n (%)
- Additional treatments given

7.4 Trial events

- Change from baseline to week 12 in best corrected distance visual acuity, mean(sd)
- Change from baseline to week 12 in central subfield thickness, mean(sd)
- Change from baseline to week 12 in central retinal sensitivity, mean(sd)
- Change from baseline to week 12 in retinal perfusion, n(%)
- Change from baseline to week 12 Total area of ischaemia, mean (sd)
- Change from baseline to week 12 in tear production, mean(sd) (study eye only)
- Change from baseline to week 12 in patient reported outcomes, mean(sd)
- Change from baseline to week 12 in ARA 290 antibodies, mean(sd)
- Adverse events, n(%)
- % of participants with ≥10 ETDRS letter gain, n(%)
- % of participants with ≥15 ETDRS letter gain, n(%)
- Change from baseline to week 12 in inflammatory biomarkers, mean(sd)
- Change from baseline to week 12 in Carbamylated Albumin, mean(sd)
- Change from baseline to week 12 in Glycosylated Albumin, mean(sd)
- Change from baseline to week 12 in HbA1C, mean(sd)

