4.3 Study Objectives

4.3.1 Primary Objective:

To determine whether ARA 290 has a beneficial effect on BCVA in people with DM and DMO.

4.3.2 Secondary Objectives:

The secondary objectives are to determine whether ARA 290 administered at a daily dose of 4mg subcutaneously for 12 weeks to patients with diabetes mellitus and DMO can improve vision (as determined by the % of participants with $a \ge 10$ and ≥ 15 ETDRS letter gain), reduce central subfield thickness, increase central retinal sensitivity, increase tear production and improve retinal perfusion and quality of life with no deleterious side effects. The effects of ARA290 on the systemic and metabolic control of participants will be also evaluated in an exploratory manner.

ARA 290 antibodies will be determined as, if they were to develop in people undergoing this treatment they could have an impact on the potential subsequent response to it.

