10.9.1 ARA 290-Antibodies

After the last subject has the week 12 blood sample taken, one of the samples (0.5ml) of serum collected will be shipped on dry ice or liquid nitrogen via courier to The Charles River Laboratory in Montreal, Canada for analysis. The additional sample (0.5ml) of serum will be stored at the research center as back-up. The samples will be stored under code, which can be linked to subject's identity only by authorised personnel.

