1. BACKGROUND AND DESIGN

The hypothesis tested is that ARA 290, when administered subcutaneously at 4mg on a daily basis for 12 weeks, due to its anti-inflammatory, anti-apoptotic and neuroprotective effects, will be of therapeutic value to patients with diabetes mellitus and diabetic macular oedema.

This will be an interventional, exploratory, investigator led, pilot study with the aim of determining if ARA 290 administered at a daily dose of 4mg subcutaneously for 12 weeks to patients with DM and severe DMO (central retinal subfield thickness measured with spectral domain optical coherence tomography of \geq 400 microns), will have a beneficial effect on improving BCVA, reducing central subfield thickness, increasing central retinal sensitivity and retinal perfusion, increasing tear production and improving quality of life with no adverse events. Data obtained in this pilot study will be used to inform future larger studies.

The primary objective is to determine whether ARA 290 has a beneficial effect on BCVA in people with DM and DMO.

The secondary objectives are to determine whether ARA 290 administered at a daily dose of 4mg subcutaneously for 12 weeks to patients with diabetes mellitus and DMO can improve vision (as determined by the % of participants with a \geq 10 and \geq 15 ETDRS letter gain), reduce central subfield thickness, increase central retinal sensitivity, increase tear production and improve retinal perfusion and quality of life with no deleterious side effects. The effects of ARA290 on the systemic and metabolic control of participants will be also evaluated in an exploratory manner.

ARA 290 antibodies will be determined as, if they were to develop in people undergoing this treatment they could have an impact on the potential subsequent response to it.

Inflammatory markers will be evaluated to investigate the potential anti-inflammatory effect of this treatment. Carbamylated albumin will be obtained as an additional measure of renal function and metabolic status and glycosylated albumin will be obtained as a confirmatory marker of glucose control.

This is a prospective, open label, interventional, single centre, investigator led, phase II study to examine the effect of ARA 290 on DMO in patients with type 1 or 2 diabetes and central retinal subfield thickness of \geq 400 microns.

The study intervention is a subcutaneous daily administration of ARA 290 in a dose of 4mg for 12 weeks

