6. ANALYSIS PRINCIPLES

In participants in whom both eyes are eligible for inclusion into the study, the eye with the better BCVA will be used as the study eye; however data will be collected and evaluated for both eyes.

Descriptive statistics will be used for the evaluation of primary and secondary outcomes. Differences in mean (SD) change from baseline for all the continuous variables investigated including visual acuity, central subfield thickness, area of retinal ischaemia, retinal sensitivity, patient reported outcome scores as well as levels of ARA 290 antibodies. Confidence intervals will also be presented. When data is not normally distributed, median (interquartile range) will be presented.

Adverse events will be presented using counts and percentages. Additionally, the % of participants with 10 or more and 15 or more ETDRS letter gain will be also reported. Data obtained at week 16 would have been similarly evaluated; however no patients required a 16-week visit.

Exploratory analysis in relation to inflammatory markers and carbamylated and glycosylated albumin will also be observed from baseline to the week 12 visit.

If the retinal perfusion image analysis is not available, it may be presented in a later report.

Additional analysis (not specified in the protocol) will be performed to explore the treatment effect in the non-study eye for (a) those patients with DMO in the non-study eye that did not fulfil the criteria for inclusion into the study (e.g. in patients with central retinal subfield thickness of < 400 microns or in patients with non-central involving DMO) and (b) patients with DMO in the non-study eye that fulfilled criteria for inclusion into the study (e.g. ≥ 400 microns).

As the analysis is only descriptive, no imputation or sensitivity analysis will be performed.

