	Macular Ischaemia	Present Absent	n(%) n(%)	Present Absent	n(%) n(%)	Extension Reduction	n(%) n(%)	Present Absent	n(%) n(%)	Present Absent	n(%) n(%)	Extension Reduction	n(%) n(%)
		N/A	n(%)	N/A	n(%)	No change	n(%)	N/A	n(%)	N/A	n(%)	No change	n(%)
						N/A	n(%)					N/A	n(%)
	Foveal Ischaemia	Present Absent	n(%) n(%)	Present Absent	n(%) n(%)	Extension Reduction	n(%) n(%)	Present Absent	n(%) n(%)	Present Absent	n(%) n(%)	Extension Reduction	n(%) n(%)
Retinal		N/A	n(%)	N/A	n(%)	No change	n(%)	N/A	n(%)	N/A	n(%)	No change	n(%)
perfusion						N/A	n(%)					N/A	n(%)
	Peripheral Ischaemia	Present Absent	n(%) n(%)	Present Absent	n(%) n(%)	Extension Reduction	n(%) n(%)	Present Absent	n(%) n(%)	Present Absent	n(%) n(%)	Extension Reduction	n(%) n(%)
		N/A	n(%)	N/A	n(%)	No change	n(%)	N/A	n(%)	N/A	n(%)	No change	n(%)
						N/A	n(%)					N/A	n(%)
	Total area of	xx.x ± xx	.x	xx.x ± xx	.x	xx.x ± xx.x		xx.x ± xx	x	xx.x ± xx	.x	xx.x ± xx.x	•
Tear produ	ischaemia iction (mm)*	xx.x ± xx	X	xx.x ± xx	. X	xx.x ± xx.x		_		_		_	
Patient	EQ5d-5L	$xx.x \pm xx$		$xx.x \pm xx$		$XX.X \pm XX.X$		-		-		-	
reported	VFQ-25	$xx.x \pm xx$.x	$xx.x \pm xx$.x	$xx.x \pm xx.x$		-		-		-	

Northern Ireland Clinical Trials Unit

outcome scores C-SSR	xx.x ± xx.x	$xx.x \pm xx.x$	xx.x ± xx.x	-	-	-
% of participants with ≥ 10 ETDRS letter gain	· -	-	n(%)	-	-	n(%)
% of participants with ≥ 15 ETDRS letter gain		-	n(%)	-	-	n(%)

^{*}Study eye only

Mean ±SD presented for continuous variables (or median [interquartile range] when appropriate) and no. (%) for categorical variables.

Table 3.2 Descriptive Statistics for Serum for ARA 290 Antibodies

Status	Timepoint	Result	n =
Screening Status	Baseline	Negative	N (%)
		Potential Positive	N (%)
	Week 12	Negative	N (%)
		Potential Positive	N (%)
Confirmatory Status	Baseline	Not Applicable	N (%)
		Negative	N (%)
		Positive	N (%)
	Week 12	Not Applicable	N (%)
		Negative	N (%)
		Positive	N (%)

Table 3.3 Exploratory Analysis (Non-Study Eye subgroups)

		Non-Study Eye (Central subfield thickness <400 microns)				Non-Study Eye(Central subfield thickness ≥400 microns)							
		Baseline		Week 12 Change		је	Baseline		Week 12		Change		
		n = ((%)	n = ((%)	n = (°	%)	n = ((%)	n = ((%)	n =	(%)
Primary outcome; best corrected distance visual acuity		$xx.x \pm xx.x$ $xx.x \pm xx.x$.X	xx.x ± xx.x		xx.x ± xx.x		xx.x ± xx.x		xx.x ± xx.x		
Central sub thickness (xx.x ± xx.x		xx.x ± xx.x		xx.x ± xx.x		xx.x ± xx.x		xx.x ± xx.x		xx.x ± xx.x	

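### The SAP text plans a mean (SD) change in ARA 290 antibodies while Table 3.2 reports status visit by visit, and the planned outputs do not guarantee a count of newly positive patients

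*SAP*

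**What the plan says.** Protocol 6.2 and SAP 2.2 make the change in ARA 290 antibodies from baseline to week 12 a secondary outcome. Protocol 4.3.2 and SAP 1 give the reason for measuring them: "if they were to develop in people undergoing this treatment they could have an impact on the potential subsequent response to it".

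The analysis is described in two ways:

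- **As a continuous variable.** SAP 7.4 lists "Change from baseline to week 12 in ARA 290 antibodies, mean(sd)". SAP 6 includes "patient reported outcome scores as well as levels of ARA 290 antibodies" among the continuous variables to be summarised by mean (SD) change, and protocol 12.3 uses the same phrase.
- **As a category.** The only antibody shell, headed "Table 3.2 Descriptive Statistics for Serum for ARA 290 Antibodies", has a screening block (Negative, "Potential Positive") and a block headed "Confirmatory Status" (Not Applicable, Negative, Positive). Each block has one set of N (%) rows for baseline and another for week 12.

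Protocol 10.9.1 covers shipment and storage of the serum. It does not say whether the laboratory returns a titre, a concentration or a status.

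**The concern.** A statistician filling the report from this SAP meets two incompatible instructions. The statistic named in 7.4 has no row in the shell, and the shell's categories cannot yield a mean and SD of change unless someone invents a numeric coding.

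The question behind the outcome is also about individuals: which patients were negative before dosing and positive at week 12? Two separate visit totals describe the group at each time and do not link a patient's two results. A stable total could reflect no change, or some patients turning positive while others turn negative. A mean change in level, if levels exist, would not count new positives either.

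At stake is whether the report can state, for a peptide given for the first time for 84 days instead of 28 (protocol 3.3), how many patients became antibody-positive.

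**Working it through.** The documents give no figure to reproduce on this point. The ten patients come without a sample size calculation (protocol 12.1, SAP 5), and the analysis is descriptive.

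**Step 1. Compare the text with the shell.**

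| Place | Type of variable | Within-patient change? |
|---|---|---|
| SAP 2.2, protocol 6.2 | not stated | yes, outcome is a change |
| SAP 7.4 | continuous, mean (SD) | yes |
| SAP 6 | continuous levels, mean (SD) change | yes |
| Protocol 12.3 | continuous levels, mean (SD) | not explicit |
| SAP Table 3.2 | categorical, N (%) | no |

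Other SAP shells do carry change. Table 3.1 has a Change column even for categorical perfusion findings (extension, reduction, no change), and Table 5 has one for every biomarker. Patient listings are promised for characteristics, visual outcomes and adverse events. Antibodies are not named in any of them.

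**Step 2. What do the Table 3.2 totals determine?** Let n patients be tested at both visits, with B confirmed positive at baseline and W at week 12. The number newly positive, x, is only bounded:

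max(0, W − B) ≤ x ≤ min(W, n − B).

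With n = 10 and illustrative B and W (the documents give no antibody rates):

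| B | W | Lower bound | Upper bound | x |
|---|---|---|---|---|
| 0 | 2 | max(0, 2) = 2 | min(2, 10) = 2 | 2 exactly |
| 1 | 3 | max(0, 2) = 2 | min(3, 9) = 3 | 2 to 3 |
| 2 | 2 | max(0, 0) = 0 | min(2, 8) = 2 | 0 to 2 |
| 3 | 3 | max(0, 0) = 0 | min(3, 7) = 3 | 0 to 3 |

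Of the 11 × 11 = 121 possible (B, W) pairs, x is undetermined when both B and W lie between 1 and 9, which is 9 × 9 = 81 pairs. It is fixed in the other 121 − 81 = 40, where B or W is 0 or 10. These are counts of arithmetical possibilities, not probabilities.

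**Step 3. How likely is a baseline positive?** The chance of at least one among ten is 1 − (1 − p)^10. For assumed p of 1%, 5% and 10% this is 9.6%, 40.1% and 65.1%. The documents give no value of p.

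**Step 4. Incomplete pairs.** Protocol 10.9 lets early leavers refuse the week-12-type evaluation, and SAP 6 rules out imputation, so the two visit blocks may rest on different patients. For example, suppose nine valid baseline results are all negative, and one of ten week 12 results is positive. Then x is 0 or 1, depending on whether the positive patient is the one without a baseline result.

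**Step 5. Could the 7.4 statistic recover the count?** A mean (SD) change in levels gives no count. If status were coded 0/1, the mean and SD of change together would identify x at n = 10. For example, two turning positive and none negative gives mean 0.2, SD 0.42; three turning positive and one negative gives mean 0.2, SD 0.63. The SAP specifies no such coding.

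**The case against.** The best defence is that Table 3.2 may be enough in practice. ARA 290 is described as first-in-class and investigational, the baseline sample precedes dosing (protocol 10.9), and recent erythropoiesis-stimulating agents and other investigational products are exclusions. Baseline positivity could well be nil. In that case, with the same patients tested at both visits, the week 12 confirmed-positive row is the answer. This stands. A reader might infer that the planned outputs can never count new positives; they can in that ordinary case, but the SAP does not ensure that it arises.

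A reader might also infer that the assay yields only a status, so that the mean (SD) cannot be computed. The documents do not establish this. The shell suggests it, but SAP 6 and protocol 12.3 speak of levels, and protocol 10.9.1 is silent on the type of result. What is certain is the conflict: if levels are reported, Table 3.2 omits the planned summary; if they are not, 7.4 cannot be carried out as written.

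A third inference would be that a planned analysis of antibodies against response is missing. The wording on possible impact explains why antibodies are measured and sets no such analysis. With sampling only at baseline and week 12, the second result coincides with the primary outcome visit, so these data could not show an effect on later response.

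Finally, both results are collected per patient, so nothing is lost and a paired count could be produced at reporting. That limits the seriousness but does not remove the conflict or supply the missing definition and denominator.

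**Conclusion.** The point holds as an inconsistency with a limited consequence. SAP 6, SAP 7.4 and protocol 12.3 treat antibodies as continuous. The only shell treats them as categories at two unlinked visits, although the outcome is defined as a change. The planned outputs therefore do not guarantee the number of patients who became positive on treatment.

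The size of the gap depends on the results. It is nil if no patient is confirmed positive at baseline and pairs are complete. With some positives at both visits the number can be left as a range, such as 0 to 2 of 10 in the assumed case of two positives at each visit. The assumptions are ten complete pairs and illustrative positive counts, since the documents give no baseline rate. The primary outcome and the sample size are unaffected. This is a reporting matter for one named secondary outcome, worth correcting because the correction is nearly free.

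**What to change.** 1. Establish from the laboratory what it reports, then make SAP 7.4, SAP 6 and protocol 12.3 agree with Table 3.2. Keep a mean (SD) or median change only if a quantitative level is reported, and in that case add a row for it to the shell.
2. Define newly positive as a valid negative result at baseline (negative on screening, or negative on confirmation after a potential positive) and confirmed positive at week 12. The denominator is patients with a valid negative baseline result and a week 12 result. Requiring a valid negative keeps a patient with no baseline sample from being counted as newly positive. Report the number excluded for want of either result.
3. Keep Table 3.2 for the two assay tiers and add a paired baseline-by-week-12 table of final status, with n/N newly positive and an exact 95% CI. SAP 6 already promises confidence intervals. With 0/10, the two-sided upper limit would be 1 − 0.025^(1/10) = 30.8%; that width reflects ten patients and not the table layout.
4. Optionally, add a per-patient antibody listing to those already planned.

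The cost is a few lines of wording and one table shell, using the samples and assay already planned.

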7.5 Toxicity/ Symptoms

- Adverse Events (AEs), Serious adverse events (SAEs), related AEs and SAES, AEs and SAEs that led to study discontinuation, and Suspected unexpected serious adverse reactions (SUSARs)
- Mortality

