Similarly, the first in human studies comprising intravenous administration of a single ascending dose and multiple ascending dose in healthy volunteers, single intravenous and subcutaneous cross-over study in healthy volunteers and in subjects with renal impairment, and intravenous repeat dose in end-stage renal disease subjects undergoing haemodyalisis raised no safety concerns. Furthermore, studies using intravenous and subcutaneous administration of ARA 290 to patients with sarcoidosis [19, 20] and type 2 diabetes mellitus [21], including studies using the same dose and route as that proposed in the current study (4 mg subcutaneous administration of ARA 290), as well as studies in patients with critical limb ischaemia, and rheumatoid arthritis have supported further the safety profile of ARA 290. No allergic reactions have been observed to ARA 290.

Specifically, two studies have been previously conducted in people with type 2 diabetes mellitus, pre-diabetes and/or drug-naïve type 2 diabetes. In both, a daily subcutaneous 4 mg dose of ARA 290 administered during a 4 week period was used. In these studies 24 and 12 patients, respectively, received ARA 290 (24 and 12 received placebo, respectively). At the dosage used, ARA 290 appeared to be safe. Adverse events were generally mild; the most common being gastrointestinal issues, sleep disturbance and headache; the frequency of adverse events was similar in both ARA 290 and placebo groups.

The dose and route of 4 mg was chosen for the current study as pharmacokinetic studies using ARA 290 demonstrated that a daily subcutaneous dose of 4 or 6 mg of ARA 290 resulted in consistent blood levels above 1-2 nM, the minimum projected exposure for efficacy [18]. The current phase 2 study however, entails for the first time prolonging the duration of treatment, from 28 days, as used in most previous studies, to 84 days. The three month duration of the ARA 290 dosage was chosen as it is expected that if treatment were to be beneficial, functional and anatomical improvements could potentially be detected in this time period but may not be seen earlier, as only patients with severe DMO (central retinal thickness of \geq 400 microns) will be included in this investigation. Furthermore, it is unlikely that a detrimental effect on vision will be observed by postponing anti-VEGF treatment for this length of time [22]

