12.3 Statistical Methods

Descriptive statistics will be used for the evaluation of primary and secondary outcomes. Differences in mean (SD) for all the continuous variables investigated including visual acuity, central subfield thickness, area of retinal ischaemia, retinal sensitivity, patient reported outcome scores as well as levels of ARA 290 antibodies. Adverse events will be presented using counts and percentages. Additionally, the % of participants with 10 or more and 15 or more ETDRS letter gain will be also reported. Data obtained at week 16 will be similarly evaluated. Exploratory analysis in relation to inflammatory markers and carbamylated and glycosylated albumin will also be observed from baseline to the week 12 visit. A Statistical Analysis Plan (SAP) will be created by the Trial Statistician, reviewed by the DMEC and approved by the CI.

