13.2 Eliciting Adverse Event Information

The PI or designee will record all directly observed AEs and all AEs spontaneously reported by the patient. In addition, the patient will be asked about AEs at each visit following initiation of treatment. The PI or designee must assess all AEs for seriousness, causality, severity and if the adverse event is related to the study drug for expectedness.

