13.5 Assessment of Severity

The PI or designee should make an assessment of severity for each AE according to the following categories:

- **Mild (Grade 1):** A reaction that is easily tolerated by the trial participant, causing minimal discomfort and not interfering with every day activities.
- **Moderate (Grade 2):** A reaction that is sufficiently discomforting to interfere with normal everyday activities.
- Severe (Grade 3): A reaction that prevents normal everyday activities.
- Life Threatening (Grade 4): A reaction that has life threatening consequences; urgent intervention indicated.
- Death (Grade 5): A reaction that results in death.

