	Psychiatric disorders	n (%)
	Metabolism and nutrition disorders	n (%)
	Infections and infestations	n (%)
	Nervous system disorders	n (%)
	Musculoskeletal and connective tissue disorders	n (%)
	Injury, poisoning and procedural complications	n (%)
	Respiratory, thoracic and mediastinal disorders	n (%)
	Skin and subcutaneous tissue disorders	n (%)
	Immune system disorders	n (%)
	Renal and urinary disorders	n (%)
	Cardiac disorders	n (%)
	Ear and labyrinth disorders	n (%)
	Investigations	n (%)

Table 4.2 Adverse event summary of system organ class & preferred term

System Organ Class / Preferred Term	Total	Adverse Reaction (AR)	Unexpected Adverse Reaction (UAR)
Patients reporting at least one adverse event	n(%)	n(%)	n(%)
General disorders and administrative site conditions	n(%)	n(%)	n(%)
Head Cold	n(%)	n(%)	n(%)
Headache	n(%)	n(%)	n(%)
Flu Symptoms	n(%)	n(%)	n(%)
Non-cardiac Chest Pain	n(%)	n(%)	n(%)
Vascular disorders	n(%)	n(%)	n(%)
Hypertension	n(%)	n(%)	n(%)
Eye disorders	n(%)	n(%)	n(%)
Drop in visual acuity	n(%)	n(%)	n(%)
Flashing lights	n(%)	n(%)	n(%)
Gastrointestinal disorders	n(%)	n(%)	n(%)
Nausea	n(%)	n(%)	n(%)
Diarrhoea	n(%)	n(%)	n(%)
Vomiting	n(%)	n(%)	n(%)
Psychiatric disorders	n(%)	n(%)	n(%)
Insomnia	n(%)	n(%)	n(%)
Metabolism and nutrition disorders	n(%)	n(%)	n(%)
Hypertriglyceridemia	n(%)	n(%)	n(%)
Hyperglycemia	n(%)	n(%)	n(%)
Metabolism and nutrition disorders - other	n(%)	n(%)	n(%)
Infections and infestations	n(%)	n(%)	n(%)
Infections – 'Other'	n(%)	n(%)	n(%)
Skin and subcutaneous tissue disorders	n(%)	n(%)	n(%)
Facial Sunburn	n(%)	n(%)	n(%)
Investigations	n(%)	n(%)	n(%)
GGT Increased	n(%)	n(%)	n(%)
Abnormal blood test results	n(%)	n(%)	n(%)

Data listings for adverse events will be included as an appendix in the final statistical report.

Table 5. Exploratory Analysis – change from baseline to 12 weeks

Exploratory Analysis	Baseline	Week 12	Change
	n=(%)	n=(%)	n=(%)
Inflammatory Markers *			
Adenosine Deaminase (ADA)	$xx.x \pm xx.x$	$xx.x \pm xx.x$	$xx.x \pm xx.x$
Artemin (ARTN)	$xx.x \pm xx.x$	$xx.x \pm xx.x$	$xx.x \pm xx.x$
Axin-1 (AXIN1)	$xx.x \pm xx.x$	$xx.x \pm xx.x$	$xx.x \pm xx.x$
Beta-nerve growth factor (BDNF)	$xx.x \pm xx.x$	$xx.x \pm xx.x$	$xx.x \pm xx.x$
Caspase 8 (CASP-8)	$xx.x \pm xx.x$	$xx.x \pm xx.x$	$xx.x \pm xx.x$
C-C motif chemokine 4 (CCL4)	$xx.x \pm xx.x$	$xx.x \pm xx.x$	$xx.x \pm xx.x$
C-C motif chemokine 19 (CCL19)	$xx.x \pm xx.x$	$xx.x \pm xx.x$	$xx.x \pm xx.x$

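### Every adverse event must be graded for severity, but no planned SAP summary shows the grade, so a non-serious, expected Grade 3 reaction that did not stop treatment looks the same as a mild one

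*SAP*

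**What the plan says.** Protocol 13.2 makes severity one of the attributes to be judged for every event: "The PI or designee must assess all AEs for seriousness, causality, severity and if the adverse event is related to the study drug for expectedness". Protocol 13.5 repeats this, "The PI or designee should make an assessment of severity for each AE according to the following categories", and gives five grades: mild, moderate, severe, life threatening and death. Grade 3 is defined as "A reaction that prevents normal everyday activities".

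On analysis, Protocol 12.3 says only: "Adverse events will be presented using counts and percentages". SAP section 6 does the same. SAP 7.5 lists "Adverse Events (AEs), Serious adverse events (SAEs), related AEs and SAES, AEs and SAEs that led to study discontinuation", together with SUSARs and mortality. In Appendix 1, Table 4.1 gives totals for AEs, ARs, SAEs, SARs, SUSARs and deaths, then AEs and SAEs by organ class. Table 4.2, titled "Adverse event summary of system organ class & preferred term", has three columns: total, adverse reaction and unexpected adverse reaction. A note below it promises adverse event listings as an appendix to the final report, without naming their fields.

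The secondary objectives (Protocol 4.3) include improving "quality of life with no deleterious side effects". The rationale (Protocol 3.3) describes two earlier four-week diabetes studies this way: "Adverse events were generally mild; the most common being gastrointestinal issues, sleep disturbance and headache". It adds that this trial lengthens treatment from the 28 days of most earlier studies to 84 days.

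**The concern.** The protocol asks for seriousness, causality, severity and, for related events, expectedness. The SAP carries three of these four attributes into its outputs and leaves out severity.

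Seriousness does not stand in for it. The seriousness criteria in Protocol 13.3 are death, threat to life, hospitalisation, disability, congenital anomaly or another important medical event. Vomiting, insomnia or headache that stops someone's daily activities but is managed at home can be Grade 3 without meeting any of them.

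The earlier safety record is itself described in terms of severity, for the same kinds of event that Table 4.2 already lists (nausea, diarrhoea, vomiting, insomnia, headache). The new feature here is exposure 84/28 = 3 times as long, and the data are meant to inform larger studies. A reader planning the next trial would want to know whether these events stayed mild. The planned summaries do not say.

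**Working it through.** The documents state no figure that depends on this point. The ten-patient sample has no alpha, power, effect size or SD behind it, so there is nothing to reproduce. The check is textual.

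**Step 1. Follow each attribute from protocol to output.**

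| Attribute required by Protocol 13.2 | SAP 7.5 | Table 4.1 | Table 4.2 |
|---|---|---|---|
| Seriousness | yes | yes | no |
| Causality | yes | yes (AR, SAR totals) | yes (AR column) |
| Expectedness | yes (SUSARs) | yes (SUSARs) | yes (UAR column) |
| Severity grade | no | no | no |

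Elsewhere in the SAP, *severe* describes the macular oedema at entry (section 1), and *severity* appears only in the name of the suicide rating scale (section 4). Neither concerns adverse events.

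**Step 2. Ask where each grade could still show.**

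- Grades 4 and 5 meet the life-threatening and death criteria, so they appear as SAEs or deaths.
- An event of any grade that ends treatment appears under SAP 7.5 and in Table 2 (reasons for early termination).
- Missed doses appear in Table 2 (doses administered), and SAP 7.3 also plans a compliance and tolerance summary.
- A related event may be classed as unexpected because of its severity (Protocol 13.6) and then falls in the UAR column. This route is optional and applies only to reactions.
- What is left is a Grade 1 to 3 event that is non-serious, not classed as unexpected, and in a patient who continues. It is counted, without its grade.

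**Step 3. Illustrate.** Suppose 4 of 10 patients have nausea that is related, expected and non-serious, and all four continue. Table 4.2 then shows total 4 (40%), AR 4 (40%), UAR 0 (0%). The row is identical if all four are Grade 1 and if all four are Grade 3.

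**Step 4. What a Grade 3 or higher row could tell us with n = 10.** The true rates here are assumptions, since the documents give none. The chance of seeing at least one such patient is 1 − (1 − p)^10:

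| Assumed true rate p | Chance of at least one in 10 |
|---|---|
| 5% | 1 − 0.95^10 = 40% |
| 10% | 1 − 0.90^10 = 65% |
| 20% | 1 − 0.80^10 = 89% |
| 30% | 1 − 0.70^10 = 97% |

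If none is seen, the exact upper limit on the true rate is 1 − 0.05^(1/10) = 25.9% (one-sided 95%) or 1 − 0.025^(1/10) = 30.8% (two-sided 95%). The row would be imprecise, but a common Grade 3 problem would probably show up in it.

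**The case against.** The case for leaving the SAP alone has real substance.

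- **Tolerability is not ignored.** SAP 7.3, Table 2 and the discontinuation item in SAP 7.5 all bear on it. This stands. A reader might infer that the outputs give no indication of tolerability, and that would be wrong. None of these items reports the grade, though, and a patient who puts up with a Grade 3 event and keeps injecting passes through all of them.
- **Non-serious severe events are not lost.** A reader might infer that they vanish from the summaries. They do not: they are counted in Table 4.1 and, by term, in Table 4.2. Only the grade is missing.
- **With ten patients, a listing may be enough.** If it shows the grade, a reader can tally it quickly. The SAP does not say that it does, nor that it does not. The fair description is *not specified*.
- **The SAP delivers what the protocol's analysis section promises.** Protocol 12.3 asks only for counts and percentages, so the two documents do not contradict each other. The shortfall is against the data the protocol requires (13.2 and 13.5), not against its analysis text.
- **Nothing here tests mildness.** It is tempting to say that the tables fail to test the earlier mild profile. No hypothesis or outcome concerns mildness, and a single-arm descriptive study of ten patients can only describe it.
- **Participant protection is unaffected.** Expedited SAE reporting and the approximately four-weekly DMEC safety reviews do not depend on these tables.

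The SAP cites ICH E3 only as a general principle and specifies no severity display, so the citation does not settle the matter either way.

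**Conclusion.** The point holds in a narrow form. Severity is a mandatory assessment for every adverse event, and no specified SAP summary or table reports it. The practical loss is confined to non-serious Grade 1 to 3 events that were not classed as unexpected and did not end treatment. These are counted, but Grade 3 cannot be separated from Grade 1. No efficacy estimate, no safety count and no in-trial safeguard changes.

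This is a cheap improvement to the reporting of a stated objective, not a defect that undermines the trial. It rests on two assumptions: that the listing cannot be relied on to carry the grade, because its fields are not specified, and that the grade is actually captured. The CRF is not among the documents. That the AE form records severity is a reasonable inference from Protocol 13.2, 13.5 and 13.8, but it is not shown.

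**What to change.** 1. In SAP 7.5 and Table 4.1, add the number (%) of patients by maximum severity grade. The minimum is two rows: patients with any Grade 3 or higher AE, and patients with any Grade 3 or higher AR.
2. State in Appendix 1 that the adverse event listing shows the grade of each event.
3. First confirm that the AE form in the CRF records the grade.

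A full grid is not needed. Table 4.2 has 18 preferred terms; four grade bands for both all AEs and ARs would add 18 × 4 × 2 = 144 cells, mostly empty with ten patients.

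The cost is a few extra rows and one listing field. If the AE form records the grade as the protocol requires, no new data are collected. No hypothesis test is added, and clinical management does not change.
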